Informed consent will be obtained from each subject before any study procedures are performed. Subjects will be evaluated for eligibility during a Screening Period of up to 21 days, during which they will continue on their pre-switch antipsychotic medication while being tapered off any prohibited medications ([Section 10.3.2](#)) in a manner that is consistent with labeling recommendations and conventional medical practices. Non-prohibited psychotropic medications other than the pre-switch antipsychotic may be continued during the study but must have been stable for at least 6 weeks prior to Screening and should be maintained at a stable dose and regimen (see [Section 10.3.1](#)).

Subjects who are being treated with two antipsychotic medications will be permitted to enter the Screening Period. At the start of Screening, the Investigator will determine which antipsychotic medication is considered “primary”, and the other one will be tapered off during the Screening Period.

Subjects who screen fail may be re-screened twice, if judged appropriate by the Investigator after discussion with the Medical Monitor. Re-screened subjects will be re-consented, assigned a new subject number, and all Visit 1 procedures will be repeated.

Open-label Treatment Period (8 weeks):

At Baseline (Day 1) (pre-switch [PS] Baseline), subjects who have successfully completed Screening and have met the eligibility criteria will begin open-label treatment with SEP-363856 while continuing to take the full dose of their pre-switch antipsychotic. SEP-363856 dosing will begin the evening of the PS Baseline visit and will continue once-daily, in the evening at bedtime, for the remainder of the Treatment Period, during which the procedures outlined in [Table 2](#) will be conducted. Subjects will be evaluated at PS Baseline and weekly throughout the rest of the study. [Section 10.3](#) describes the circumstances and specifications for which prior and concomitant psychotropic medications other than the pre-switch antipsychotic are allowed in this study.

Subjects will receive SEP-363856 50 mg/day from Day 1 through Day 3 and 75 mg/day from Day 4 through Day 7. Every effort should be made to maintain subjects at 75 mg/day from Day 4 through Day 7. Beginning on Day 8, the dose of SEP-363856 can be adjusted in increments of 25 mg among 3 dose levels (50, 75 and 100 mg), according to the following requirements:

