- The SEP-363856 dose should be increased to 100 mg/day on Day 8 to help ensure adequate coverage of symptoms, provided there are no significant tolerability problems as judged by the Investigator. Dose increases are to be made no more frequently than weekly to the next highest dose level (in 25 mg increments). Increases in dose will occur at regularly scheduled study visits, when possible. Dose increases between regularly scheduled visits may occur after prospective approval by the Medical Monitor. If a dose increase is performed between regularly scheduled visits, subjects will be required to return to the clinic at an unscheduled visit for drug dispensation.
- SEP-363856 dose reductions can be made to the next lowest dose level (in 25 mg increments) at any time beginning on Day 8 for safety and intolerance issues as

judged by the Investigator. If a dose decrease is needed between study visits, subjects will be asked to return to the clinic for an unscheduled visit for drug dispensation.

Beginning on Day 8, the Investigator is permitted to start tapering the subject's pre-switch antipsychotic (further guidelines are provided in [Section 21](#) Appendix II). The Investigator has the discretion to complete the discontinuation of the pre-switch antipsychotic by the end of Weeks 2, 3, 4, 5, or 6. As outlined in [Section 10.3.4](#), concomitant medications for the treatment of extrapyramidal symptoms (EPS) and akathisia will be tapered during the antipsychotic tapering period. Once the pre-switch antipsychotic has been fully discontinued, subjects will remain on SEP-363856 (50 to 100 mg/day) until the end of Week 8.

For subjects who have received study drug and who prematurely discontinue from the study treatment, every effort should be made to complete procedures within 48 hours of the last study drug dose at the end of treatment (EOT)/early termination (ET) visit.

Subjects who complete the 8-week Open-label Treatment Period will be eligible to participate in a separate open-label extension study (Study SEP361-309). Subjects who early terminate (ET) from the SEP361-308 study are not eligible to enroll in SEP361-309.

Follow-up Period (1 week):

Subjects who take any dose of SEP-363856 then discontinue early from the study or complete study and do not enter the extension study (Study SEP361-309) will be required to complete the Follow-up Visit 7 days (\pm 2 days) post last dose of study drug.

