- **Not related** - Improbable temporal relationship and is plausibly related to other drugs or underlying disease.

- **Related**

- **Possible** - occurred in a reasonable time after study drug administration but could be related to concurrent drugs or underlying disease.
 - **Probable** - occurred in a reasonable time after study drug administration, is unlikely to be attributable to concurrent drugs or underlying disease, and there is a plausible mechanism to implicate the study drug.
 - **Definite** - occurred in a reasonable time after study drug administration and cannot be explained by concurrent drugs or underlying disease. The adverse event should respond to dechallenge/rechallenge however, this is not mandatory before assigning a definite causality.

The Medical Monitor is the initial contact person for protocol related questions or discussion of AEs. The contact information for the Medical Monitor as well as other emergency contact information can be found in [Table 1](#) of this protocol.

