17.3.3. RELATIONSHIP TO STUDY MEDICATION

Relationship to study medication, as indicated by the Investigator, is classed as "not related"/ "possible"/ "probable"/ "definite" (increasing strength of relationship). A "related" AE is defined as an AE with a relationship to study medication as "possible", "probable" or "definite". AEs with a missing relationship to study medication will be regarded as related to the study medication. For this summary, AEs will be presented in 2 categories, related and not related.

If a subject reported an AE more than once within the same SOC/ PT in different relationship categories, the subject will be assigned to a category for that SOC/ PT based on the worst case relationship (i.e., strongest relationship). Event counts will not be included in this summary.

In separate tables, study medication-related AEs will be summarized by SOC and PT and summarized by PT.

Document: PPD

Author: PPD

Version Number:

1.0

Version Date:

06MAY2024

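### Read literally, Protocol 12.3 rates an AE with reasonable timing and a clear other cause as Possible, which the plan counts as related; the related-AE tables should show all four collected levels

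*Protocol*

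**What the plan says.** Protocol 12.3 gives the investigator four causality ratings:

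- *Not related*: "Improbable temporal relationship and is plausibly related to other drugs or underlying disease".
- *Possible*: "occurred in a reasonable time after study drug administration but could be related to concurrent drugs or underlying disease".
- *Probable*: the timing is again reasonable, another drug or illness is an improbable explanation, and a mechanism for the study drug exists.
- *Definite*: "occurred in a reasonable time after study drug administration and cannot be explained by concurrent drugs or underlying disease". A dechallenge or rechallenge response is expected but not required.

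Neither document defines a reasonable time or an improbable one. SAP 17.3.3 takes the rating as the investigator gives it.

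Protocol 15.3.5.2 and SAP 17.3.3 group *Possible*, *Probable* and *Definite* as related, and treat a missing rating as related. The SAP adds: "For this summary, AEs will be presented in 2 categories, related and not related". A subject with several ratings inside one SOC or PT is counted under the strongest. The related category feeds the overall incidence summary, its subgroup repeats and a listing (SAP 17.3), and tables by SOC and PT and by PT alone (SAP 17.3.3).

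On exposure, Protocol 7.1 says that at Baseline subjects "will begin open-label treatment with SEP-363856 while continuing to take the full dose of their pre-switch antipsychotic". Dosing of SEP-363856 "will continue once-daily, in the evening at bedtime, for the remainder of the Treatment Period". Taper of the old drug may start on Day 8, and "The Investigator has the discretion to complete the discontinuation of the pre-switch antipsychotic by the end of Weeks 2, 3, 4, 5, or 6".

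**The concern.** *Not related* needs both limbs: timing that does not fit and another plausible cause. The second limb alone is not enough. If the timing fits and the investigator believes that the old antipsychotic, its withdrawal or a viral illness is responsible, the only wording that describes the event is *Possible*, and *Possible* is tabulated as related.

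Two design features make this more than a drafting point. The drug is taken every evening, so an on-treatment AE will often start soon after a dose. And a competing drug cause is present by design: every subject starts on two antipsychotics and then comes off one. Under Protocol 10.3.4, medication for EPS is tapered alongside it.

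The study has one arm and no control, so the causality rating is one of the few within-study indications of which AEs investigators attribute to SEP-363856. If the rating scale cannot record a well-timed event as due to something else, the related-AE tables move towards the all-AE tables, and a two-category display does not show how much of the related count is only *Possible*.

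**Working it through.** The plan states no figure on this point, so there is none to reproduce. The check is to apply the four definitions to every combination of the features they use.

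**Inputs (all from Protocol 12.3).** Timing: reasonable or improbable. Other drug or disease cause: plausible, unlikely, or unable to explain the event. Mechanism for the study drug: plausible or not. That gives 2 × 3 × 2 = 12 combinations.

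| Timing | Other drug or disease cause | Mechanism | Rating that fits | Tabulated as |
|---|---|---|---|---|
| Reasonable | Plausible | Yes | Possible | Related |
| Reasonable | Plausible | No | Possible | Related |
| Reasonable | Unlikely | Yes | Probable | Related |
| Reasonable | Unlikely | No | None | – |
| Reasonable | Cannot explain | Yes | Probable or Definite | Related |
| Reasonable | Cannot explain | No | Definite | Related |
| Improbable | Plausible | Yes | Not related | Not related |
| Improbable | Plausible | No | Not related | Not related |
| Improbable | Unlikely | Yes | None | – |
| Improbable | Unlikely | No | None | – |
| Improbable | Cannot explain | Yes | None | – |
| Improbable | Cannot explain | No | None | – |

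**Counts.** Related 5, not related 2, no rating 5; 5 + 2 + 5 = 12. Of the 6 reasonable-timing rows, 0 reach *Not related*: 2 are *Possible*, 3 are *Probable* and/or *Definite*, and 1 has no rating. Of the 6 improbable-timing rows, 2 are *Not related* and 4 have no rating. These are counts of combinations, not expected frequencies of AEs.

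**The rows that matter.** A well-timed event with a clear drug or disease explanation sits in the first two rows. No other section of either document lets it be *Not related*.

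**Accidents.** No rating is written for an external cause, because the definitions name only drugs and disease. A well-timed accident for which drug and disease are thought unlikely, with no mechanism, falls in the fourth row and has no rating. (If drug and disease are ruled out altogether, the only literal match is *Definite*, which cannot be intended.) If the field is then left blank, the missing-data rule counts the event as related.

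**Timing under this regimen.** With one dose each evening and full compliance, any on-treatment onset lies within about 24 hours of the previous dose. Whether that makes the timing reasonable is not stated.

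**Where the rating is used.**

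| Output | Uses relationship? | Source |
|---|---|---|
| Primary and secondary endpoints | No | Protocol 6.1, 6.2; SAP 17.1, 17.2 |
| All-AE tables | No | SAP 17.3.1 |
| AEs leading to discontinuation or drug withdrawal | No | SAP 17.3.4, 17.3.5 |
| SAE reporting to 30 days after last dose | No | Protocol 12.4.1 |
| SAE reporting beyond 30 days | Yes (at least possibly related) | Protocol 12.4.1 |
| Related-AE summaries, tables and listing | Yes | Protocol 15.3.5.2; SAP 17.3, 17.3.3 |

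**The case against.** The strongest reply has four parts.

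**Judgement is left to the investigator.** Timing can be judged on latency, incubation, a prodrome before dosing or onset during an interruption, not only on hours since the last tablet. AEs up to 9 days after the last dose are also summarised. So the definitions are incomplete guidance rather than a mechanical rule. This stands. A reader might infer that almost every on-treatment AE has to be at least *Possible*. The documents do not support that: a reasonable time is undefined, and one of the six reasonable-timing combinations has no rating at all.

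**Counting doubtful events as related is conservative.** Missing relationship is counted as related and missing severity as the highest, so the grouping fits the plan's general approach. The objective is also the safety of switching, so events of the cross-taper are part of what is studied, and Protocol 4.3 acknowledges that coadministration during the taper is not well characterised. When either drug could be responsible, *Possible* is a fair description. This stands for truly ambiguous events. It does not answer the case where the investigator thinks the other cause is clearly the more likely one and has no rating with which to say so.

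**The reach is narrow.** This stands, as the last table shows.

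**Changing the definition now is awkward.** SAP 3.4 records 101 subjects enrolled, and SAP 3.5 puts the first screening in December 2022. A new definition would not re-rate recorded AEs and could mix two definitions in one dataset. This stands, and it limits the fix.

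**Conclusion.** The point holds in a limited form. By its wording, Protocol 12.3 closes *Not related* to any AE with reasonable timing, however clear the other cause; where that cause is a drug or disease, the AE is *Possible* and is counted as related. Some events, accidents among them, have no rating that fits. With nightly dosing and a planned cross-taper, this can overstate the study-medication-related AE summaries.

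The size cannot be computed from the documents. A reader might want a multiplier: if a share *s* of subjects with any AE had only AEs better explained by another cause, and all were nevertheless rated related, the overstatement would be 1/(1 − *s*), which is 1.3 at *s* = 25% and 4 at *s* = 75%. Neither document gives *s*, and the formula assumes that investigators apply the wording mechanically, so the result only restates the assumption. It should not be quoted as an effect in this trial.

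The conclusion rests on two assumptions: that at least some investigators follow the definitions as written, and that they regard onset soon after a nightly dose as reasonable timing. The four levels are collected and a related-AE listing is planned, and the output templates are not among the documents, so it would go too far to say that the split within related is unrecoverable. It is simply not part of the specified summary. This is worth correcting but does not threaten the study's main conclusions.

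**What to change.** **Do now.** In SAP 17.3.3, and in Protocol 15.3.5.2 if it is amended, tabulate not related, possible, probable and definite beside the related / not related split, keeping the strongest-relationship rule. State the Protocol 12.3 definition in the table footnote and in the study report, including that *Not related* required improbable timing together with a plausible other drug or disease cause. This uses data already collected and leaves the two-way split in place. The cost is a longer descriptive table.

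**Do only if AEs are still to be assessed, or when the wording is reused.** Reword *Not related* so that either improbable timing or a more likely other cause is enough, and let the other cause include one that is neither a drug nor a disease. Say what counts as a reasonable time. Do not reclassify AEs already recorded; if both definitions are used in this study, report which one applied to each AE. The cost is a protocol amendment with sponsor and IRB/IEC approval (Protocol 17.5), revised CRF guidance, and a less conservative related rate.

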12.4. Immediately Reportable Events

The following medical events must be immediately reported to the Sponsor:

- SAE
- Pregnancy

Emergency contact information can be found in Table 1.

12.4.1. Serious Adverse Event

If the Investigator or study center staff becomes aware of a SAE that occurs in a study subject after first administration of study drug through 30 days following the last dose of the study drug, this must be reported immediately to the Sponsor whether considered related or unrelated to the study drug. SAEs that occur from the signing of the ICF up to the last visit must be recorded on the CRF and the data recorded should agree with those on the SAE form. In addition, pretreatment events that meet the definition of serious ([Section 12.1.2](#)) should be reported following the same guidelines.

Should the Investigator become aware of an SAE greater than 30 days post last dose, the Investigator or an authorized delegate should report SAEs “spontaneously” to PPD-PVG if considered at least possibly related to the study drug.

SAEs will be followed until resolution, loss to follow-up, stabilization of condition, or the event is otherwise explained.

An initial or follow-up SAE form as applicable must be completed and signed and sent via fax or email (see [Table 1](#)) to PPD-PVG immediately but not more than 24 hours after the Investigator or study center staff become aware of the event. Response to specific questions included on the SAE form for psychiatric SAEs is required. The SAE form must be signed by the Investigator or appropriate designee. The Sponsor provides the SAE form used to report SAEs.

The Sponsor or designee will promptly notify all study centers and Investigators of an SAE that is determined to be expedited to the Regulatory Authorities in accordance with applicable law(s) and regulation(s). These SAEs must be promptly reported to the Institutional Review Board (IRB) or Independent Ethics Committee (IEC) by the Investigator or the appropriate person at the study center if required per IRB/IEC guidelines.

12.4.2. Pregnancy

Pregnancies that occur from the time that informed consent is signed through 90 days following the last dose of the study medication will be collected and reported on the Pregnancy Event Form.

If a subject becomes pregnant during the course of the study, she will be instructed to commence discontinuation of the study medication. Further, the subject will be instructed to return to the study center within 48 hours of the first notification of pregnancy and undergo a serum pregnancy test, as confirmation of pregnancy. If positive, the female pregnant subject will no longer receive any additional study medication. All pregnancies, whether or not the subject received any additional study medication, will be followed until resolution (ie, termination [voluntary or spontaneous] or birth). Infants may be followed for up to one year following birth.

If a pregnancy is reported for a study subject's partner from time of subject's first dose to 30 days post last dose, the subject's partner may be asked to sign a consent form to allow the Sponsor to follow her pregnancy. The Sponsor's representative will provide instructions on how to collect pregnancy information in accordance with local requirements. Proper consent to collect the partner's information will be obtained before the collection of any information.

To report a pregnancy, the Pregnancy Event Form must be completed and sent via fax to PPD-PVG immediately but no more than 24 hours after the Investigator or study center staff becomes aware of the pregnancy. The Sponsor provides the Pregnancy Event Form.

Pregnancy itself is not regarded as an AE unless there is a suspicion that the study drug may have interfered with the effectiveness of a contraceptive medication or other AEs were detected.

13. TERMINATION OF SUBJECT FROM STUDY

13.1. Criteria for Subject Termination

Subjects may be discontinued from study participation / the study drug at any time for any of the following reasons. The possible reasons for termination of study participation / study drug are as follows:

- Adverse event
- Lack of efficacy (specify)
- Lost to follow-up (specify)
- Withdrawal by subject (specify)
- Non-compliance with study drug (specify)
- Protocol deviation (specify)
- Death
- Pregnancy
- Other (specify)

If at any time during the course of the study, in the opinion of the Investigator, the subject may no longer safely participate due to a change in medical status (eg, experiences an AE, becomes pregnant), the subject must be discontinued from the study drug. Subjects discontinued from study drug will be discontinued from the study.

The reason for discontinuation of “Lack of efficacy” should be selected when a subject early terminates from the study because there has been insufficient therapeutic benefit of the study drug (perceived or actual) and the subject’s baseline condition has neither worsened nor improved significantly.

The reason for study drug discontinuation will be recorded on the appropriate CRF. In case of death, the date of death should be captured on the CRF. Subjects who prematurely terminate the study participation will not be replaced.

13.2. Clinical Assessments After Study Drug Discontinuation

Subjects who have not received any study drug will not be followed up on leaving the study.

For subjects who have received study drug and who prematurely discontinue from the study treatment (ie, do not complete through Week 8), every effort should be made to complete the final evaluation procedures, in accordance with the ET visit described in [Section 11.9.10](#).

Subjects who complete the study but do not elect to enroll in the open-label extension study (Study SEP361-309) and those subjects who discontinue the study early will complete a follow up visit 7 (± 2) days after the last dose of study drug as described in [Section 11.9.11](#).

14. STUDY TERMINATION

The Sponsor reserves the right to discontinue the study at this study center or at multiple centers for safety or administrative reasons at any time while safeguarding that early termination does not compromise subjects' safety or well-being. In particular, a study center that does not recruit at an acceptable rate may be closed. Should the study be terminated, and/or the study center closed for whatever reason, all documentation and study medication pertaining to the study must be returned to the Sponsor or its representative.

If, in the opinion of the Investigator, clinical observations suggest it may be unsafe to continue, the Investigator may terminate part or the entire study after consultation with the Sponsor.

In the event of study or site termination, subjects undergo final evaluation procedures in accordance with the early termination (ET) visit described in [Section 11.9.10](#) and safety Follow-up Visit as described in [Section 11.9.11](#).

